### **Baseline**

For the endpoint of interest, the baseline is defined as the last non-missing assessment taken prior to the first infusion of the first dose of study IP. In cases where baseline assessments are taken on the same day as the first infusion of the first dose of IP, and either no times are reported or the IP and assessment times are the same, it will be assumed that these assessments are taken prior to IP being administered. For subjects who are randomized but not dosed after the randomization, the baseline is defined as the last non-missing assessment prior to or on the date of randomization.

For the ADA analysis following the 1st infusion of the 2nd dose, the baseline is defined as last non-missing assessment prior to the 1st infusion of the 2nd dose.

### **Binding and Neutralizing ADA status During First Dose Period**

Subjects will be considered to have negative binding ADA status during first dose period if subjects had negative binding ADA

- from baseline up to 1st infusion of 2nd dose for subjects who received 2nd dose, or
- from baseline up to week 24 (day 175) or EOS (whichever is earlier) for subjects who didn't receive 2nd dose.

Subjects will be considered to have positive binding ADA status during first dose period if subjects had positive binding ADA status at any time point

- up to the 1st infusion of the 2nd dose for subjects who received 2nd dose, or
- up to week 24 (day 175) or EOS (whichever is earlier) for subjects who didn't receive 2nd dose.

The same definition applies to subjects' neutralizing ADA status. Subjects with a binding negative or no result at baseline and at least one post baseline will be included in this derivation.

### **Change from Baseline**

Change from baseline is defined as (value at post-baseline visit – value at baseline).

### **Completed Study**

A subject is considered to have completed the study if they indicated they completed study on the EOS eCRF.

Sponsor: Amgen Inc.

Statistical Analysis Plan

Protocol No: 20130108

10-December-2018/ Version 2.0

### **Concomitant and Prior Medication**

Prior medications are defined as medications with a stop date prior to the first infusion of the first dose of study IP. Concomitant medications are defined as any medications ongoing at the start of IP treatment or with a start date on or after the first dose date.

### **Duration of IP Exposure**

For subjects who received 2nd dose of IP, the duration of IP exposure will be derived as min (EOS date, analysis data cutoff date) minus date of first IP exposure + 1 day.

For subjects who didn't receive 2nd dose of IP, the duration of IP exposure will be derived as min (EOS date, week 24 [day 175], analysis data cutoff date) minus date of first IP exposure + 1 day.

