8.4.3 Withdrawal and Replacement of Subjects

8.4.3.1 Criteria for Subject Withdrawal

Subjects have the right to withdraw from the study at any time and for any reason without prejudice to future medical care by the physician or at the institution.

Subjects (or a legally acceptable representative) can decline to continue receiving investigational product and/or other protocol required therapies or procedures at any time during the study, but continue participating in the study. If this occurs, the Investigator is to discuss with the subject the appropriate processes for discontinuation from investigational product or other protocol required therapies and must discuss with the subject the options for continuation of the Schedule of Assessments and Procedures ([Table 1](#)) and collection of data, including endpoints and AEs. The Investigator must document the change to the Schedule of Assessments ([Table 1](#)) and the level of follow-up that is agreed to by the subject (eg, in person, by telephone/mail, through family/friends, in correspondence/communication with other physicians, from review of the medical records).

Withdrawal of consent for a study means that the subject does not wish to receive further protocol-required therapies or procedures, and the subject does not wish to or is unable to continue further study participation. Subject data up to withdrawal of consent will be included in the analysis of the study, and, where permitted, publicly available data can be included after withdrawal of consent. The Investigator is to discuss with the subject appropriate procedures for withdrawal from the study.

Reasons for removal from protocol-required investigational products or procedural assessments might include:

- subject request to end IP administration
- safety concern (eg, due to an AE, failure to follow contraception, and/or protocol requirements)
- pregnancy

Reasons for removal of a subject from the study might include:

- withdrawal of consent from study
- lost to follow-up
- decision by Sponsor

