### Exposure Adjusted Incidence Rate (EAIR) for Adverse Events and Adverse Event of Interest

The exposure adjusted incidence rate is defined as the number of subjects with a particular AE divided by the total exposure-time among subjects in the respective treatment group at risk of an initial occurrence of the event. Specifically,

$$\text{Exposure Adjusted Incidence Rate} = \frac{n}{T} = \frac{n}{\sum t_i},$$

where  $n$  is the number of subjects with events,  $t_i$  is a subject's exposure time under a given unit and  $T$  is the total exposure time under a given time unit of the subjects in the group. If a subject has multiple events, the  $t_i$  is the time from the first dose date of the respective treatment to the onset of the first event. For those subjects who crossed over from one IP treatment during the 1st dose to another IP treatment during the 2nd dose, the exposure time following each of the doses will be counted in the respective treatment

Sponsor: Amgen Inc.

Statistical Analysis Plan

Protocol No: 20130108

10-December-2018/ Version 2.0

---

group. For a subject with no event, the *ti* is set to the total exposure time duration of IP exposure (as defined in [Section 5.1](#)) for that subject.

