### **Treatment-emergent Adverse Event**

A treatment-emergent AE (TEAE) is defined as an AE that begins or increases in severity or frequency at or after the first study IP administration through EOS. If the AE starts on the same day as the first dose of IP, then the flag indicating whether the AE started prior to the first dose on the adverse event CRF page will be used.

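### For subjects without a second dose who stay on study past day 175, the entire-study exposure-adjusted rates count first events to end of study but end event-free time at day 175

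*SAP*

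**What the plan says.** **Exposure duration (SAP 5.1, Duration of IP Exposure).** With a second dose it is "min (EOS date, analysis data cutoff date) minus date of first IP exposure + 1 day". Without one it is "min (EOS date, week 24 [day 175], analysis data cutoff date"), less the first exposure date, plus one day, so at most 175 days.

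**EAIR (SAP 5.4).** The numerator "is the number of subjects with events". The denominator sums each subject's time t_i and is described as time among subjects at risk of a first occurrence. With no event, t_i "is set to the total exposure time duration of IP exposure", with a reference back to SAP 5.1. With an event, t_i "is the time from the first dose date of the respective treatment to the onset of the first event". The SAP words this for subjects with multiple events; I read it as covering a single event too. No day-175 limit is attached to it.

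**Events counted (SAP 5.4, Treatment-emergent Adverse Event).** An event qualifies if it begins or worsens "at or after the first study IP administration through EOS". Subjects without a second dose are not excepted.

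**Reporting (SAP 9.8.1 and Appendix 6).** The EAIR is produced for the entire study, with a rate ratio and 95% CI between ABP 798 and the reference product. Tables 14-6.7.1 and 14-6.7.2 run from Day 1 through End of Study.

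**Who can be affected (Protocol 8.4.3.1).** Subjects may decline further investigational product "but continue participating in the study". The investigator is then to discuss continued assessments and data collection, including adverse events.

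**The concern.** A person-time rate needs the same window above and below the line. Here the day-175 limit applies only to event-free subjects who had no second dose. Take two such subjects, both followed to day 337. One has a first event on day 250 and adds one event and about 250 days. The other has no event and adds 175 days. Having the event enlarges the denominator, and the event-free subject's days 176 to 337 vanish, although an event on any of them would have been counted. This contradicts the SAP's own description of the denominator as time at risk.

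The error runs one way: the rate is too high. The rate ratio is biased as well if the proportion staying on study without a second dose differs between products. Comparing safety is a stated secondary objective, and this ratio is one of its between-product summaries.

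**Working it through.** The plan states no EAIR, event rate or number of affected subjects, so there is no figure of its own to reproduce. The check is of the definition and of the size it can reach.

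**1. Do the windows match anywhere?** SAP 9.8 defines two safety periods. For subjects without a second dose, the first ends at day 175 or EOS, whichever is earlier, so events and time agree there. The second is the entire study, without that limit, and the EAIR is tabulated only for the second. Nothing in the SAP removes events after day 175 from the EAIR numerator.

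**2. Time dropped per event-free subject.** This is (EOS day − 175) when EOS is later than day 175, otherwise zero.
- Upper end: EOS at week 48, target day 337: 337 − 175 = 162 days, or 162/337 = 48% of that subject's follow-up.
- Low end: the subject stops at the week 24 visit (target day 169) and has the EOS visit within the 14 days in Protocol 8.4.3.2: 169 + 14 = 183, and 183 − 175 = 8 days.

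**3. Share of an arm's person-time.** Let f be the share of the arm on study past day 175 without a second dose. No document gives f; 3% to 10% is assumed. With 337 days as the base per subject, the share lost is f × days dropped/337.

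| f | 8 days dropped | 162 days dropped |
|---|---|---|
| 3% | 0.07% | 1.4% |
| 10% | 0.24% | 4.8% |

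The base matters. SAP 5.4 books time after a change of product to the new product, so a rituximab (US) column holding mainly first-dose time would have a smaller base and a larger share. The table shells are not in the SAP text.

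**4. Effect on the rate.** Assume a constant hazard λ per year, follow-up to T and the cap at C = 175 days (times in years).
- Expected number with an event, per subject: 1 − exp(−λT).
- Consistent expected time: [1 − exp(−λT)]/λ, which returns λ exactly.
- Expected time under the SAP rule: the same, less exp(−λT)·(T − C).

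Example, λ = 0.1 and T = 337 days: λT = 0.0923, so 0.0881 events are expected. Consistent time is 0.881 years. The SAP rule drops 0.912 × 162/365.25 = 0.404, leaving 0.477. The rate is 0.0881/0.477 = 0.185 against a true 0.1, a factor of 1.85 among affected subjects.

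For T = 337 days, with the rest of the arm also followed to day 337:

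| λ per year | Factor, affected subjects | Arm level, f = 5% | Arm level, f = 10% |
|---|---|---|---|
| 0.02 | 1.91 | 1.024 | 1.050 |
| 0.1 | 1.85 | 1.024 | 1.048 |
| 0.5 | 1.61 | 1.019 | 1.039 |
| 1.0 | 1.41 | 1.015 | 1.030 |

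Inflation falls as the event rate rises, because fewer subjects remain event-free to have time removed. With EOS at day 203 the factor among affected subjects is 1.12 to 1.16, and the arm-level inflation is at most about 1.3% even at f = 15%.

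**5. Effect on the ratio.** With equal true rates, follow-up to day 337, and 15% of one arm affected against 5% of the other, the expected ratio is 1.03 to 1.05 instead of 1.00.

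**The case against.** The best counter-argument concerns size and reach, and most of it stands.

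- **Many who stop treatment will leave soon after.** Protocol 8.4.3.2 puts the EOS assessments within 14 days of withdrawal. Section 8.5.7.5 places alternative treatment after a termination visit. Section 8.5.7.1 has subjects no longer eligible for study treatment complete the EOS assessments before additional therapy. For such subjects the gap is days, or nil if EOS falls by day 175. Protocol 12.6.7.2 also limits treatment-emergent events to 28 days after the last dose when a subject discontinues the study early; the SAP definition does not carry this over.
- **The planned dropout is not the affected group.** A reader might take the 15% dropout by week 24 from the sample-size section as the share affected. Those subjects' EOS would normally precede day 175, where both clocks stop together.
- **The ratio is imprecise anyway.** With, say, 20 subjects with an event per arm and equal person-time (assumption), the 95% limits around a ratio of 1 are exp(±1.96 × √(1/20 + 1/20)), or 0.54 to 1.86. A shift to 1.03 to 1.05 is small beside that.
- **The cap may be deliberate.** Day 175 also closes the first-dose period for antibody status and safety summaries, and a rate per unit of exposure might be meant to exclude off-drug time. That is a legitimate aim, but it requires the same limit on events, and none is stated.

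None of this removes the mismatch for a subject who stays on study past day 175.

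**Conclusion.** The definition is wrong as written for one group: subjects without a second dose whose EOS falls after day 175. Their post-day-175 events enter the entire-study EAIR and their post-day-175 event-free time does not. The rate is biased upward, and the ratio is biased if the share of such subjects differs between arms.

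The size cannot be fixed from the documents. With an assumed 3% to 10% affected and 337 days per subject as the base, lost person-time lies between about 0.07% to 0.24% (EOS near day 183) and an upper bound of about 1.4% to 4.8% (all followed to day 337). A reader might take the 48% or the 4.8% as the expected size; both require follow-up to week 48 in every affected subject, which the withdrawal rules make unlikely for many of them.

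A reader might also infer that the safety comparison as a whole is compromised. The documents do not support that. The protocol summarizes safety descriptively and treats exposure-adjusted rates as optional, no decision rule uses them, and crude subject incidence, which does not use this denominator, is tabulated as well. The primary PK and efficacy analyses are untouched. This is a minor inconsistency, worth correcting because it is cheap.

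**What to change.** Separate at-risk time for the EAIR from duration of IP exposure. In SAP 5.4, state that for the entire-study EAIR the time of a subject without the event ends at the earlier of the EOS date and the analysis data cutoff date, whether or not a second dose was given. This matches the treatment-emergent window and keeps the cutoff limit already in SAP 5.1. Leave the day-175 cap in place for the exposure summary and the first-dose-period summaries.

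If on-treatment exposure is what is intended, the equally consistent alternative is to count first events only to day 175 in subjects without a second dose and censor t_i there. The table titles would then need to say so, since they now read as covering the whole study.

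Under either rule and the constant-hazard model above, the expected rate equals the true rate. The cost is one SAP sentence and one change to the derivation. Reporting, by treatment group, how many subjects without a second dose had an EOS date after day 175 would show how much the choice matters.

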### **Early Retreatment**

If 1st infusion of 2nd dose is administered prior to Study Day 162, subjects are considered as receiving early retreatment.

### **End of Study Date**

EOS date is the date recorded on the End of Study page of the eCRF for a randomized subject.

### **First Dose Date**

The date on which a subject is administered the first infusion of first dose of study IP. This date is also referred to as Study Day 1.

### **Infusion delay**

If an IP administration form for a visit is entered with an infusion administered of NONE and a reason for delay/not administered, and also there is infusion information entered on a subsequent IP form, that subject is considered having an infusion delay.

There is one exception. If the second infusion of the 1st dose is delayed for such a large extended period that it falls at week 16 or after, the infusion will be entered in the week 24 folder. In this case, the Day 15 IP infusion will be considered missing instead of delayed.

### **Infusion missed**

When a subject with an IP administration form entering an infusion administered of NONE and a reason for delay/not administered but there is no subsequent IP form with infusion information, the subject is considered to have missed an infusion at that visit.

In addition, if the second infusion of the 1st dose is delayed for such a large extended period that it falls at week 16 or after, the infusion will be entered in the week 24 folder. In this case, the Day 15 IP infusion will be considered missing.

### **Last Dose Date**

The date on which a subject is administered the last infusion of the last dose of study IP.

Sponsor: Amgen Inc.

Statistical Analysis Plan

Protocol No: 20130108

10-December-2018/ Version 2.0

### **Percent Improvement from Baseline**

For endpoints where higher scores indicate greater severity, the percent improvement from baseline is: (value at baseline – value at post-baseline visit) X 100 / (value at baseline).

For endpoints where lower scores indicate greater severity, the percent improvement from baseline is: (value at post-baseline visit – value at baseline) X 100 / (value at baseline).

If the baseline value is 0 and the post-baseline value is also 0, then the percent improvement from baseline is set to 0. If the baseline value is 0 and the post-baseline value is non-zero, then the percent improvement from baseline is set to “missing” (or ‘.’).

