### 5.3 EFFICACY

#### **ACR20/50/70**

The ACR composite score evaluates clinical improvement relative to an initial assessment for clinical trials in subjects with RA.

The ACR20 response is defined as at least 20% improvement compared to baseline for both swollen and tender joint counts (66/68 joint counts), as well as for at least 3 out of the following 5 additional parameters:

- Subject's Global Health Assessment
- Investigator's Global Health Assessment
- Subject's assessment of pain
- Health Assessment Questionnaire Disability Index (HAQ-DI)
- C-Reactive Protein (CRP)

ACR50 and ACR70 are defined in a similar fashion to ACR20 but require at least 50 and 70 percent improvement respectively. Method for handling missing data is described in the appendix 2.

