#### **DAS28-CRP**

The DAS28-CRP is a composite measure of disease activity in RA. It is a continuous measure based on 28 DAS joints from the ACR, the Subject's Global Health Assessment score, and CRP, as follows:

$$\text{DAS28-CRP} = 0.56*(\text{TJC28})^{0.5} + 0.28*(\text{SJC28})^{0.5} + 0.36*\ln(\text{CRP}+1) + 0.014*\text{SGH} + 0.96$$

where TJC28 is the tender joint count of the 28 joints in the DAS, SJC28 is the swollen joint count of the 28 joints in the DAS, CRP is in mg/L, and SGH is the Subject's Global Health Assessment in 0 to 100 scale.

If the CRP is at a non-detectable level, then replace it with the minimum detectable level.

Sponsor: Amgen Inc.

Statistical Analysis Plan

Protocol No: 20130108

10-December-2018/ Version 2.0

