### **Hybrid ACR Response**

Hybrid ACR response is a continuous score of the mean improvement in the core set measures combining the ACR20, ACR50, and ACR70 response rates.

The hybrid ACR can be calculated when all 7 components are available following the table below ([American College of Rheumatology Committee to Reevaluate Improvement Criteria, 2007](#)):

ACR Status	Mean % change in all 7 core set measures			
	<20	>=20, <50	>=50, <70	>=70
Not ACR20	Mean % change	19.99	19.99	19.99
ACR20 but not ACR50	20	Mean % change	49.99	49.99
ACR50 but not ACR70	50	50	Mean % change	69.99
ACR70	70	70	70	Mean % change

If a core set measure worsens by > 100% , the percentage change will be limited to 100%.

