## APPENDIX 2 METHOD FOR MISSING INDIVIDUAL COMPONENTS OF ACR CALCULATION

In the case of some ACR components are missing, the ACR composite scores will be based on the non-missing components. If a subject's non-missing components are not sufficient to identify ACR composite score, then that subject will be considered as missing ACR response. The corresponding algorithm is listed below (using ACR 20 as an example):

- If both Tender or Swollen Joint Counts are improved at least 20%, and
  - If three or more of the other five ACR components are improved at least 20%, the subject is an ACR 20 responder;
  - If three or more of the other five ACR components are not improved at least 20%, the subject is an ACR 20 non-responder;
  - If none of the above, the ACR response for the subject cannot be determined due to missing data and is therefore coded as missing.
- If either swollen or tender joint counts is not improved at least 20%, the subject is an ACR non-responder
- If either swollen or tender joint counts is missing and the other improved at least 20%,  
and
  - If three or more of the other five ACR components are not improved at least 20%, the subject is an ACR 20 non-responder;
  - Otherwise, the ACR response for the subject cannot be determined due to missing data and is therefore coded as missing

Sponsor: Amgen Inc.

Statistical Analysis Plan

Protocol No: 20130108

10-December-2018/ Version 2.0

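### A non-joint ACR component that worsens from a baseline of 0 is set to missing, so some definite ACR20/50/70 non-responders leave the as-observed analysis

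*SAP*

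**What the plan says.** SAP 5.1 treats a zero baseline in two ways. If the component stays at zero: "If the baseline value is 0 and the post-baseline value is also 0, then the percent improvement from baseline is set to 0". If it moves away from zero: "If the baseline value is 0 and the post-baseline value is non-zero, then the percent improvement from baseline is set to" missing.

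SAP 5.3 gives the responder rule: "The ACR20 response is defined as at least 20% improvement compared to baseline for both swollen and tender joint counts", together with at least three of five further components (subject's global, investigator's global, pain, HAQ-DI, CRP). ACR50 and ACR70 have the same structure with higher thresholds.

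SAP Appendix 2 covers incomplete data: "In the case of some ACR components are missing, the ACR composite scores will be based on the non-missing components". With both joint counts improved, three or more improved components make a responder, and three or more not improved make a non-responder. Otherwise "the ACR response for the subject cannot be determined due to missing data and is therefore coded as missing".

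For the continuous score, SAP 5.3 states: "The hybrid ACR can be calculated when all 7 components are available following the table below".

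SAP 9.7.2 analyses ACR20/50/70 as observed. SAP 9.7.4 determines response from the data available at each visit and gives no non-responder imputation. Its tipping-point analysis covers DAS28-CRP only.

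**The concern.** The five non-joint components all run from good (low) to bad (high). When one goes from 0 to a positive value, the ratio is undefined but the clinical fact is not: the component was measured and got worse. The responder rule needs only a yes or no on improvement, and the answer is no.

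Setting it to missing gives an inverted result. A subject whose HAQ-DI stays at 0 has that component counted towards non-response. A subject whose HAQ-DI rises from 0 does not. If that component decides the outcome, Appendix 2 cannot classify the subject, who leaves the denominator. Because the component can never have improved, the rule can only remove non-responders.

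ACR20/50/70 are named secondary efficacy endpoints (SAP 4.2.2), reported as risk ratios and risk differences with confidence intervals. What is at stake is a small upward bias in these rates.

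**Working it through.** The documents give no figure that depends on this rule, so there is none to reproduce. The check applies SAP 5.1 and Appendix 2 to every possible pattern.

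**Can missing be read as not improved in Appendix 2?** No. With five components each either improved or not, at least three always fall on one side. The undetermined branch could then never occur, so its presence shows that a missing component counts on neither side.

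**Which components are exposed?** Protocol 8.4.1 requires at least 6 swollen and 6 tender joints at screening and baseline, so joint counts of 0 are not expected. It sets no minimum for HAQ-DI, pain or the globals. Protocol 8.4.2 excludes only functional Class IV, so a subject with little disability can enter.

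**Enumeration, both joint counts improved.** Let W be the number of components that worsen from 0. The remaining 5 − W are each improved or not. The logical coding counts W as not improved; the SAP coding counts W as missing.

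| W | Patterns | Responder (both codings) | Logical non-responder | Of these, missing under SAP |
|---|---|---|---|---|
| 0 | 32 | 16 | 16 | 0 |
| 1 | 16 | 5 | 11 | 6 |
| 2 | 8 | 1 | 7 | 6 |
| 3 | 4 | 0 | 4 | 4 |

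For W = 1, the six recoded patterns are those in which exactly 2 of the other 4 improved: 4!/(2!·2!) = 6. No responder pattern changes in any row.

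**Worked case.** Joint counts improved, two components improved, two not improved, HAQ-DI from 0 to 0.5. Three of five are not improved, so the subject is an ACR20 non-responder. Under the SAP the count is 2 against 2 with one missing, and the response is coded missing. Had HAQ-DI stayed at 0, the SAP would code non-responder.

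**Size.** If p is the response rate with everyone classified and f the share recoded to missing, the observed rate is p/(1 − f).

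- p = 50%, f = 0.5%: 0.50/0.995 = 50.3%
- p = 50%, f = 2%: 0.50/0.98 = 51.0%
- p = 30%, f = 2%: 0.30/0.98 = 30.6%
- p = 70%, f = 2%: 0.70/0.98 = 71.4%

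The range for f is an assumption. Suppose 2 to 5% of subjects have one component that rises from 0, and each other component improves independently with probability q between 0.5 and 0.7. The chance that exactly two of four improve is 6q²(1 − q)² = 0.375 at q = 0.5 and 0.265 at q = 0.7. Then f lies between 0.02 × 0.265 = 0.5% and 0.05 × 0.375 = 1.9%. That is before multiplying by the chance that both joint counts improve, which lowers it further.

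**Hybrid ACR.** Six components at +40% and one going 0 to 0 give 240/7 = 34.3. The same subject with the seventh going from 0 to a positive value has no score. SAP 5.3 limits a worsening of more than 100% ("the percentage change will be limited to 100" percent), but SAP 5.1 leaves no percentage to limit.

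**The case against.** Percent change from 0 is undefined, and setting it to missing is a recognised convention. That stands for the hybrid score, which needs a number. It does not stand for ACR20/50/70, which need only a classification that the data already settle.

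Zero baselines should be uncommon. Entry requires at least 6 swollen and 6 tender joints and a raised ESR or CRP. A 0 on either global means no disease activity (Protocol 17.4), and the physician scoring the investigator's global can see the joint assessments (Protocol 10.1). Exposure is mainly HAQ-DI and perhaps pain. This stands, and it is why the effect is called small.

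Four stronger readings are tempting, but the documents do not support them.

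- *Hybrid means are biased upward.* A dropped subject may score high or low. For illustration, score the worsened component −100%. Six others at +80% give (480 − 100)/7 = 54.3, which the SAP 5.3 table turns into 70 for an ACR70 responder; dropping that subject lowers any group mean below 70. Six at +45% give (270 − 100)/7 = 24.3, and dropping that subject raises any mean above it.
- *The comparison hides differential worsening.* SAP 9.9.2 summarises every ACR component by treatment and visit, as observed, and SAP 9.9.1 adds change from baseline for the DAS28-CRP components. Absolute worsening from 0 enters those tables. An equal recoded share in each arm also leaves the risk ratio unchanged, because 1/(1 − f) cancels.
- *CRP falls under the same rule.* SAP 5.3 does give its substitution only under DAS28-CRP ("If the CRP is at a non-detectable level, then replace it with the minimum detectable level"). Nothing shows that CRP is ever recorded as 0, so this is missing detail.
- *The cap on worsening is wrong because it is printed without a minus sign.* It plainly limits a worsening; the sign is clerical.

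**Conclusion.** The ACR20/50/70 derivation is wrong as written for one identifiable group: both joint counts improved, at least one non-joint component worsened from 0, and that component decides the classification. These subjects are definite non-responders, are coded missing, and nothing later in the SAP restores them. Any resulting bias in the response rates is upward.

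The size is not given in the documents and is probably small: about 0.3 to 1.0 percentage points on a 50% rate if 0.5 to 2% of subjects are recoded. That range rests on an assumed frequency of zero baselines and on independent components.

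For hybrid ACR, loss of the score is certain for any subject with such a component, but the direction of the effect on the mean is undetermined.

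ACR20/50/70 and hybrid ACR are declared descriptive (SAP 9.7.2 and 9.7.3). The DAS28-CRP equivalence test uses absolute change from baseline, and the PK endpoints do not use this rule. No formal conclusion of the trial depends on the point.

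**What to change.** Add one sentence to SAP 5.1 and one to Appendix 2: for ACR20/50/70, a component on which higher is worse, with baseline 0 and a post-baseline value above 0, is coded as not improved. With this coding, the 16 patterns for one such component become 5 responders, 11 non-responders and none missing, instead of 5, 5 and 6.

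The cost is two sentences and one derivation change, with no new data. Reported response rates will be slightly lower, because the recoded subjects return to the denominator.

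The correction does not extend to hybrid ACR. Giving such a subject −100% would assign the maximum penalty to a move as small as 1 mm on a VAS, which is a debatable scoring choice rather than a repair.
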